## CLINICAL PROTOCOL

SPONSOR: ZMS

PROTOCOL: ZMS-1500-Pa2023

## 6 DEVICE MANAGEMENT

### 6.1 UNPACKING AND INSPECTION

It is the responsibility of the Principal Investigator (PI) to ensure that all study devices are unpacked and inspected prior to using in any study procedures. Upon arrival, the Investigator or designated study personnel will remove the device display monitor and accessories from the shipping container; ensure all device components are received. The study site must inform the Sponsor of any missing or damaged items within seven (7) days. Devices with any missing or damaged items cannot be used and shall be replaced.

### 6.2 ACCOUNTABILITY, STORAGE & DISPENSATION

It is the responsibility of the Principal Investigator to ensure all study devices are inventoried and accounted for throughout the conduct of the study. The Investigator or qualified designated study personnel will record all information on the Device Accountability forms maintained in the Investigator Site Files (ISF).

The investigational device will be stored at the study center. When not in use, the device will be stored in a secure location (i.e., area with limited access or in a locked cabinet) under appropriate environmental conditions found in the Instructions for Use (IFU) manual.

The study device shall only be used under the supervision of the Principal Investigator or designated study personnel on authorized study subjects.

### 6.3 CLEANING & RETURN

The study devices shall be cleaned before each use. Cleaning procedures will be followed per the Instructions for Use (IFU) manuals. The study devices and any unused accessories will be returned to the Sponsor after study completion.

## 7 RISKS & BENEFITS

### 7.1 RISK DETERMINATION & REDUCTION

This study is determined to be non-significant risk. An Investigational Device Exemption will not be submitted based on this determination.

Study subjects are subject to risk no greater than or similar to risks associated with undergoing a standard blood donation. The use of the CM-1500 does not meet the definition of significant risk under 21CRF 812.3 (m). All adverse events will be recorded and analyzed to evaluate their significance. Possible risks may include:

- [Possible, Rare] Skin irritation could occur from the electrodes
- [Possible, Mild] Discomfort could occur due to lying in a supine position for duration of the donation procedure.

## CLINICAL PROTOCOL

SPONSOR: ZMS

PROTOCOL: ZMS-1500-Pa2023

Every possible effort will be made to reduce the risks to a minimum. Investigators or qualified designated study personnel will be experienced and skilled in blood donation procedures, receive training on the protocol and use of the device. All adverse events will be documented and reported to the Sponsor.

### 7.2 BENEFITS

This study is for research purposes only. There is no direct benefit to subjects participating in the study. Information from this study may help other people in the future.

## 8 SAFETY ASSESSMENT AND MANAGEMENT

Safety will be assessed by reviewing and summarizing adverse events.

### 8.1 SAFETY DEFINITIONS

#### 8.1.1 ADVERSE EVENT (AE)

An Adverse Event (AE) is defined as any untoward medical occurrence, whether or not related to the study device or study procedure. AE's are characterized by grading, actions taken, relationship to donation or study procedure, and outcome. These definitions are in the corresponding tables below. All adverse events related to the blood donation procedure will be recorded and reported in addition to those that may occur specific to the protocol-defined study procedure. All attempts should be made to ensure resolution of the adverse event upon study completion.

Table 1: Adverse Event Severity Grading

Severity	Description
Grade 1: Mild	Awareness of signs or symptoms, but they are easily tolerated
Grade 2: Moderate	Enough discomfort to cause interference with usual activity
Grade 3: Severe	Incapacitating, with the inability to work or do usual activity
Grade 4: Fatal	Subject expired/death occurred

Table 2: Adverse Events Action(s) Taken

Action Taken (Check all that apply)	Description
None	No actions were taken, observation only.
Medications	Subject required medication(s)
Other Treatment	Subject required other treatment(s)
Early Withdrawal	Adverse event led to early study withdrawal

## CLINICAL PROTOCOL

SPONSOR: ZMS

PROTOCOL: ZMS-1500-Pa2023

Table 3: Adverse Event Relationship to Blood Draw or Study Procedure

Relationship	Description
None	Causal relationship can be ruled out
Possible – Donation Procedure	Causal relationship is reasonably possible to the blood draw procedure (i.e., the relationship cannot be ruled out)
Possible – Study Device	Causal relationship is reasonably possible to the study device (i.e., the relationship cannot be ruled out)
Yes – Donation Procedure	Causal relationship to the blood draw procedure is certain
Yes – Study Device	Causal relationship to the study device is certain

Table 4: Adverse Event Outcome

Outcome	Description
Recovered/Resolved	Subject recovered and event was resolved upon study completion
Recovered/Resolved with Sequelae	Subject recovered but exhibited lingering minor symptoms upon study completion
Recovering	Adverse event persisted upon study completion but was improving
Not Recovered	Adverse event persisted upon study completion and was not exhibiting any signs of improvement
Death	Subject expired
Unknown	Status of the adverse event was unknown upon study completion

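### Table 3 has no code for the study procedure, although its title and Section 8.1.1 require that attribution, so an adverse event caused by the assigned position cannot be coded to its own cause

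*Combined protocol and SAP*

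**What the plan says.** Section 8.1.1 sets the rule: "AE's are characterized by grading, actions taken, relationship to donation or study procedure, and outcome". It then sends the reader to the tables for the meaning of each item: "These definitions are in the corresponding tables below".

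The same section keeps three possible sources of an event apart. An AE counts "whether or not related to the study device or study procedure", which names device and study procedure as two things. Donation-related events are to be recorded "in addition to those that may occur specific to the protocol-defined study procedure", which separates the donation from the study procedure.

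The table that should supply the relationship codes is headed "Table 3: Adverse Event Relationship to Blood Draw or Study Procedure". Its rows are None, Possible – Donation Procedure, Possible – Study Device, Yes – Donation Procedure and Yes – Study Device. None is defined by "Causal relationship can be ruled out".

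Section 8.1.2 applies the same relationship assessment to serious adverse events (SAEs). Section 7.1 lists two possible risks: skin irritation from the electrodes and, separately, "Discomfort could occur due to lying in a supine position for duration of the donation procedure".

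**The concern.** The table's title and its rows disagree. The title promises the blood draw and the study procedure; the rows deliver the blood draw and the study device. The device is in the rows but not in the title, and the study procedure is in the title but not in the rows.

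The gap falls on the factor being studied. The primary objective concerns the effect of subject position, and position is what this protocol assigns on top of an ordinary donation. Section 7.1 foresees an event of that kind. An investigator who follows Table 3 as written has no code for it. The relationship field, which is meant to record judged cause, would then give some other cause or none.

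**Working it through.** No figure is at issue, so the check sets the passages side by side.

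**Step 1. Count the rows of Table 3 by cause.** All five rows are legible, so this is not a redaction or a broken table.

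| Cause | Required by Section 8.1.1 or the table title? | Rows in Table 3 |
|---|---|---|
| None | – | 1 |
| Donation procedure / blood draw | Yes, both | 2 (Possible, Yes) |
| Study device | Named in 8.1.1 as a separate term; not in the title | 2 (Possible, Yes) |
| Study procedure | Yes, both | 0 |

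Total: 1 + 2 + 2 + 0 = 5.

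**Step 2. Ask whether an existing row can be read to include the study procedure.** Section 8.1.1 works against this. It names the device and the study procedure separately, and it has study-procedure events recorded in addition to donation events. Widening either pair of rows to take in the study procedure would go against that wording.

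**Step 3. Test the clearest case.** Under Section 5.2 the needle is placed and the line is clamped. The chair is then moved to the position assigned at enrollment, and the subject stays there for at least ten minutes before baseline is recorded. Suppose discomfort arises in that interval because of the position:

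- Study Device rows: not true, because the device did not cause it.
- Donation Procedure rows: no blood is being drawn. The code could be defended only by pointing to the needle already in the arm, which is not the cause supposed here.
- None: requires that a causal relationship be ruled out. Under a table whose title covers the study procedure, it cannot be.

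No row is correct for this event.

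**Step 4. Test the less clear case.** For supine discomfort during the draw, Possible – Donation Procedure asks only that a relationship cannot be excluded. That code is coarse but defensible. The gap therefore does not make every position-related code false; it means that no such event can be coded to position itself.

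**Step 5. See what survives.** Section 5.4 has AEs recorded from consent to completion whatever their attribution, and the assigned position is known for each subject. Counts by position can therefore be recovered, and what is lost is the judged cause. Section 9.3 specifies no AE tabulation, either by position or by relationship; Section 8 says only that AEs are reviewed and summarized.

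**The case against.** The best case on the other side is that this is a labelling slip with little consequence. Much of that stands. Several stronger conclusions that a reader might draw are not supported:

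- **Every position-related event is misclassified.** Section 7.1 itself ties supine discomfort to the duration of the donation, and the Possible – Donation Procedure row can fairly hold an event during the draw.
- **The effect of position on safety is hidden.** AEs can be compared between 180° and 135° without using Table 3 at all. In a non-blinded study (Section 2.3), an investigator's opinion on cause would in any case be a weak measure of that effect.
- **The exploratory objective is compromised.** In Section 2.1 that objective relates AEs to demographics, parameter changes and timing. It does not call on the relationship code.
- **The device's safety profile is misstated.** Nothing directs sites to code positional discomfort to the device, and Section 7.1 lists electrode irritation separately.
- **A related-event rate is distorted by a stated amount.** No such rate is a planned output. One event divided by the group size does not say how often misattribution would occur.

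The CRF is also not among the documents and may offer a further option. If it does, it departs from the protocol's own definitions, and the two still need to agree.

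None of this removes the contradiction between the table's title, its rows and Section 8.1.1, or supplies a correct code for the settling-period event.

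**Conclusion.** The point holds as an internal inconsistency of minor weight. Section 8.1.1 and the title of Table 3 require attribution to the study procedure, and the table has no row for it. An event caused by the assigned position must go to donation, device or None. By reference from Section 8.1.2, the same is true of SAEs.

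Its size is limited to causal attribution. The AE record and the counts by assigned position are intact, and the documents give no basis for estimating how many events would be affected. The one positional risk they list is tagged as possible and mild.

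The conclusion rests on two assumptions: that positioning belongs to the study procedure, as its assignment by the protocol suggests, and that sites code from Table 3 as printed.

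**What to change.** - Add two rows to Table 3: *Possible – Study Procedure (including positioning)* and *Yes – Study Procedure (including positioning)*. Make the same change on the CRF if it mirrors the table.
- Add the device to the table's title, so that title, rows and Section 8.1.1 name the same three causes. Section 8.1.2 then needs no separate change beyond consistent wording.
- State in Section 9.3 that AEs will be summarized by assigned position and by relationship.

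The cost is two rows, a title edit and one descriptive table. There are no added subject procedures and no change in sample size. It does need a protocol amendment, which under Section 11.2 requires sponsor approval and prior written IRB approval. It is best made before events are coded, because judged cause is hard to reconstruct afterwards.

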### 8.1.2 SERIOUS ADVERSE EVENT (SAE)

An SAE is defined as an AE that meets any of the following criteria: Fatal or life-threatening\*; requires or prolongs in-subject hospitalization\*\*; results in persistent or significant disability/incapacity; congenital anomaly/birth defect; important medical event. An event's severity grading, action(s) taken, relationship to the donation or study procedure, and the outcome will all be used for SAE's.

\*Life-threatening is defined as an event in which the subject was at risk of death at the time of the event. It does not refer to an event that hypothetically may have caused death if it was more severe.

\*\*In-subject hospitalization is defined as an event in which the subject was admitted to the hospital for one or more days, even if released on the same day or an emergency room visit, which results in admission to the hospital. Emergency room visits that do not result in admission to the hospital should be evaluated for one of the other serious outcomes criteria.

### 8.1.3 UNANTICIPATED ADVERSE DEVICE EFFECT (UADE)

An unanticipated adverse device effect is defined by 21 CFR 812.3 as any serious adverse effect on the health or safety or life-threatening problem or death caused by or associated with, a device, if that effect, problem, or death was not previously identified in nature, severity, or degree of incidence in the investigational plan or application (including supplementary plan or application, or any other unanticipated serious problem associated with the device that relates to the rights, safety, or welfare of

## CLINICAL PROTOCOL

SPONSOR: ZMS

PROTOCOL: ZMS-1500-Pa2023

subjects. The Investigator or designee will indicate if they believe an event was an unanticipated adverse device effect on the case report form, and the Sponsor will evaluate for reporting requirements defined below.

### 8.2 SAFETY REPORTING

Safety reporting begins at the time of signed Informed Consent and ends at subject study completion.

Investigators shall submit to the Sponsor a report of any AE's or SAE's that occur during the study within five (5) working days but no later than ten (10) days after the Investigator learns of the event.

Investigators shall submit to the Sponsor a report of any UADE(s) that occur during the study as soon as possible but no later than five (5) working days after the Investigator learns of the effect. Sponsors will evaluate UADE's.

#### 8.2.1 REPORTING EVENTS & SAFETY CONTACTS

Events will be reported, in writing, to the Sponsor as soon as possible but no later than five (5) working days after the Investigator learns of the event. In an event resulting in the death of the subject, the event will be reported within 24-hours of knowledge of the event. The Sponsor is responsible for fulfilling IRB and regulatory reporting requirements.

Table 5: Study Reporting Contacts

Contact	Contact Information
Sponsor Representative	[REDACTED]
IRB	[REDACTED]
Mailing Address	[REDACTED]

## 9 STATISTICAL METHODS AND CONSIDERATIONS

### 9.1 SAMPLE SIZE DETERMINATION

This study is designed as a feasibility study to evaluate the effect of subject positioning on the individual parameters and Relative Index (RI) during minor blood loss in the form of a 1 unit (~500mL) whole blood draw. No statistical hypotheses have been generated for this study; therefore, the sample size of up to 60

## CLINICAL PROTOCOL

SPONSOR: ZMS

PROTOCOL: ZMS-1500-Pa2023

participants is empirically determined to be sufficient for an early-phase hypothesis-generating study and is based on clinical judgment rather than statistical considerations.

### 9.2 DATASETS ANALYZED

All eligible subjects who were enrolled in the study and connected to the study devices will be included in the analyses. Subjects who withdraw after enrollment and before the study devices are connected will be excluded from the analyses.

### 9.3 STATISTICAL ANALYSIS

#### 9.3.1 DESCRIPTIVE STATISTICS

Continuous data will be summarized in terms of the mean, standard deviation (SD), median, quartiles, minimum, maximum, and number of observations, unless otherwise specified. Categorical data will be summarized in terms of the number of subjects providing data at the relevant time point (n), frequency count, and percentage. Percentages will be calculated using n as the denominator.

#### 9.3.2 STATISTICAL METHOD FOR CONTINUOUS VARIABLES

The normality of continuous data will be assessed both visually and by Shapiro-Wilk test. If data are considered normally distributed, the 95% CI of the mean will be constructed based on a t-distribution. Otherwise, if data are skewed, distribution-free confidence interval of the median will be calculated. The comparison between before and after blood donation will be conducted by using paired t-test or Wilcoxon signed-rank test, depending on the distribution of data.

#### 9.3.3 DEMOGRAPHIC AND BASELINE CHARACTERISTICS

All baseline demographic variables collected at enrollment will be summarized using descriptive statistics.

#### 9.3.4 PRIMARY ANALYSIS

The following will cover the planned primary analyses for this study procedure. Unless otherwise specified, statistical analyses will be performed using two-sided hypothesis tests at the overall 5% significance level. No multiple comparison adjustments will be performed.

##### 1. Analysis of measurements taken before and after blood draw

Measurements including RI and individual physiological parameters taken before and after blood draw will be first summarized using descriptive statistics. For each parameter, the absolute and percent differences before and after draw will be calculated and summarized using summary statistics together with 95% confidence interval. The p-value will be calculated using paired t-test or Wilcoxon signed-rank test to compare with zero.

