## 2 INVESTIGATIONAL PLAN

### 2.1 OBJECTIVES

The primary objective of the study is to examine the effects of subject positioning on the ability of the CM-1500 parameters to detect minor blood loss.

Exploratory objectives of the study will include:

- Compare the performance of the CM-1500 monitoring during a whole blood donation with subjects positioned in either a fully supine position (180°) or in a reclined position (approx. 135°)
- Investigate any possible correlations between adverse events, subject demographics, changes in the individual parameters, and timing of when the events occurred.

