### 2.4 STUDY ENDPOINTS

The study endpoints include the change and percentage of change between measurements before and after blood draw in the Relative Index, individual parameters and standard physiological parameters. The change is defined as the value after draw minus the one before draw. The percentage of change is the change value divided by the value before draw. Other endpoints such as area under receiver operating characteristic (ROC) together with sensitivity and specificity at various thresholds are also derived for the Relative Index, individual parameters and each of standard physiological parameters in detecting in detecting minor blood loss (i.e., ~500mL).

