### 4 SUBJECT POPULATION AND SELECTION

#### 4.1 POPULATION AND ANTICIPATED NUMBER OF SUBJECTS

Up to 60 healthy adult subjects who meet the inclusion and exclusion criteria will be enrolled in the study. A minimum of 20 subjects will be enrolled at each of the subject positionings (180° and 135°). Every reasonable effort will be made to achieve a 50:50 split between the two subject positionings.

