##### 2. Analysis of differences between measurement taken before and after blood draw.

The difference between measurements taken before and after blood draw will be calculated by value before donation minus value after draw for RI and each individual physiological parameter.

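### The primary objective is the effect of subject position, but the analysis sections plan no summary, estimate or comparison of 180° against 135°

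*Combined protocol and SAP*

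**What the plan says.** Section 2.1 states: "The primary objective of the study is to examine the effects of subject positioning on the ability of the CM-1500 parameters". The ability in question is detection of a small blood loss. The section then lists the supine-versus-reclined comparison again, as an exploratory objective. Section 9.1 repeats the purpose: "This study is designed as a feasibility study to evaluate the effect of subject positioning on the individual parameters and Relative Index (RI"), and adds that there are no statistical hypotheses and that the sample size rests on clinical judgment. Recruitment is built on the two positions. Section 4.1 says "A minimum of 20 subjects will be enrolled at each of the subject positionings (180° and 135"°), with a 50:50 target and up to 60 subjects in all.

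The analysis text does not take this up:

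- Section 9.2: "All eligible subjects who were enrolled in the study and connected to the study devices will be included in the analyses". No position groups are defined.
- Section 9.3.2: "The comparison between before and after blood donation will be conducted by using paired t-test or Wilcoxon signed-rank test". This is the only comparison method in the section.
- Section 9.3.3 summarizes baseline variables and does not say by position.
- Section 9.3.4 item 1 summarizes absolute and percent change with a 95% CI, then: "The p-value will be calculated using paired t-test or Wilcoxon signed-rank test to compare with zero".
- Section 9.3.4 item 2: "The difference between measurements taken before and after blood draw will be calculated by value before donation minus value after draw". This covers RI and every parameter, and nothing follows the definition.

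The table of contents ends Section 9 at 9.3.4. Section 2.4 names the endpoints: "The study endpoints include the change and percentage of change between measurements before and after blood draw in the Relative Index". It extends them to the device's separate parameters and to standard physiological measures, and adds ROC area, sensitivity and specificity, for which 9.3 has no analysis.

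**The concern.** The stated primary analysis answers a different question from the stated primary objective. Item 1 asks whether readings change after about 500 mL is drawn. The objective asks whether that change, or the ability to detect it, depends on position.

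Item 1 does not say whether it is run on all subjects or by position, and neither reading is enough. On all subjects, it cannot reveal a position effect. By position, it gives two separate tests against zero and no estimate of the difference between them.

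A statistician will no doubt produce some position comparison in the end. Unless it is fixed first, the choices of mean or median, absolute or percent change, and adjusted or unadjusted would be made with the data in hand. The study is unblinded and non-randomized, and the plan makes no multiplicity adjustment.

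**Working it through.** **Text check.** Position is the study question in 2.1 and 9.1 and the enrolment structure in 4.1. In 9.2, 9.3.1, 9.3.2, 9.3.3 and both items of 9.3.4 it does not appear. No two-sample method, model or stratified summary is named. The number of planned position estimates is zero.

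The plan has no figure to reproduce: 9.1 gives no SD, effect size or power. The calculations below show scale only. Every SD and mean change in them is an assumption.

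**Item 1 on all subjects.** Take 30 per position and a within-position SD of 1. With position means m1 and m2 and overall mean m:

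- overall SD = sqrt{[2×29×1 + 30(m1−m)² + 30(m2−m)²]/59}
- SE = SD/√60, and t(0.975, 59) = 2.001

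| Mean change 180° / 135° | Overall mean | Overall SD | 95% CI | p | 135° minus 180° |
|---|---|---|---|---|---|
| −0.5 / −0.5 | −0.50 | √(58/59) = 0.991 | −0.76 to −0.24 | 0.0002 | 0 |
| −1.0 / 0 | −0.50 | √(73/59) = 1.112 | −0.79 to −0.21 | 0.0009 | +1.0 |
| 0 / −1.0 | −0.50 | 1.112 | −0.79 to −0.21 | 0.0009 | −1.0 |

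The last two rows have opposite position effects and identical item 1 output.

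**Item 1 by position.** Take observed mean changes of −0.5 (180°) and −0.25 (135°), SD 1, 30 each. SE = 1/√30 = 0.183 and t(0.975, 29) = 2.045.

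- 180°: CI −0.87 to −0.13, p = 0.010
- 135°: CI −0.62 to 0.12, p = 0.18

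One test is significant and the other is not, which invites the conclusion that position matters. The difference is 0.25. With the 30/30 half-width below (0.52), its CI is −0.27 to 0.77 and includes zero.

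**Precision of the missing contrast.** Welch half-width = t(0.975, Satterthwaite df) × sqrt(s1²/n1 + s2²/n2).

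| n per position | SDs | df | Half-width |
|---|---|---|---|
| 30/30 | 1, 1 | 58 | 2.002 × 0.258 = 0.52 |
| 20/40 | 1, 1 | 38.1 | 2.024 × 0.274 = 0.55 |
| 20/20 | 1, 1 | 38 | 2.024 × 0.316 = 0.64 |
| 18/18 | 1, 1 | 34 | 2.032 × 0.333 = 0.68 |
| 16/16 | 1, 1 | 30 | 2.042 × 0.354 = 0.72 |
| 30/30 | 1, 1.5 | 50.5 | 2.008 × 0.329 = 0.66 |
| 20/20 | 1, 1.5 | 33.1 | 2.034 × 0.403 = 0.82 |

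Units are the SD of change, or the smaller SD where they differ. The 18/18 and 16/16 rows are included because 20 is a minimum enrolled, not a minimum evaluable. Section 4.4 provides for replacing subjects who withdraw before using the device and is silent on later losses. The documents give no attrition rate.

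Precision for an AUC difference is not calculated, because it depends on a within-subject correlation that the documents do not state.

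**The case against.** The strongest reply is that this is a feasibility study. Section 9.1 calls it hypothesis-generating and disclaims hypotheses, and 2.1 labels the direct comparison of positions exploratory. Position is assigned at enrolment, so the contrast can be produced at any time. That excuses the absence of a powered test. It does not excuse the absence of any estimate for the stated objective, and the plan is not purely descriptive, since 9.3.4 already specifies two-sided tests and p-values. The primary and exploratory labels in 2.1 overlap, and neither version has an analysis.

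A second reply is that 9.2 does not actually say the positions are pooled, so item 1 could be run by position. That is correct, and the three-case illustration applies only to the pooled reading. The by-position reading still gives no difference and no interval for one.

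A third is that the objective speaks of detection, so ROC measures are more direct than mean change. This has some force, and the ROC endpoints belong in the fix. Leading with change is still sound: 2.4 lists change first, and 9.1 speaks of the effect on the parameters and RI.

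Finally, adjusted models and similar extras go beyond the defect. They are optional.

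**Conclusion.** The concern holds. The primary objective has no planned analysis, and under either reading of item 1 the plan yields no estimate of the position effect. This rests on the text alone, not on any assumed number, and it should be corrected before analysis.

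The planned size allows a position contrast, but a wide one: a 95% CI half-width of roughly 0.5 to 0.7 SD of change for equal SDs and 16 to 30 evaluable subjects per position, and up to 0.82 of the smaller SD at 20/20 if one SD is 1.5 times the other. No figure in the documents is contradicted.

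**What to change.** Complete Section 9.3.4 item 2, for example:

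> For RI, each individual parameter and the standard physiological parameters, change (after minus before, as in 2.4) and percent change will be summarized by assigned position. The 135° minus 180° difference in mean change will be reported with a two-sided 95% CI (Welch). If changes in either position are judged skewed under 9.3.2, medians will be shown for both positions and the difference in medians added with a 95% bootstrap CI, resampling subjects within position.

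This keeps the mean difference available for every parameter and applies one rule to both positions. An estimate with a CI is enough, since 9.1 disclaims hypotheses. In addition:

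- Report the 2.4 ROC endpoints by position, with before-draw readings as negatives and after-draw readings as positives, and give the AUC difference with a CI bootstrapped by subject.
- Show baseline data and volume drawn by position, and call the result an association, because 2.3 states the study is non-randomized.
- Group by assigned position (5.2) and list subjects repositioned because of a reaction (5.3).
- State in 2.1 whether the position comparison is primary or exploratory.
- If an adjusted sensitivity analysis is wanted, name the model now, for example a linear model with position, age, gender, previous donation and donation-anxiety score.
- As a separate minor point, 2.4 defines change as after minus before and item 2 as before minus after. Use one convention.

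**Cost.** A protocol amendment before analysis, with the sponsor and IRB approval that 11.2 requires, and modest extra analysis. No new data or subjects are needed. The intervals will be visibly wide. RI plus five parameters on two scales already gives 6 × 2 = 12 unadjusted intervals, and the standard physiological parameters, medians and AUC differences add more, so all must be read as descriptive.
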